9. EFFICACY EVALUATION

9.1 Overview of Efficacy Analysis Issues

9.1.1 Handling of Dropouts or Missing Data

Missing data will not be replaced.

9.1.2 Assessment Time Windows

Rules for assessment time windows are addressed in Section 9.2 for each efficacy endpoint.

9.2 Analysis Methods

9.2.1 Primary Efficacy Analyses

The primary efficacy endpoint is the CFA assessed at the end of each 3-week treatment period (Visit 6 or Visit 9). CFA is evaluated by the 72-hour marker-to-marker stool sample collection (1 measure at Visit 6 and 1 at Visit 9) and standardized high-fat diet during each supervised confinement. Coefficient of fat absorption represents the percentage of fat absorbed from the diet by the subject and is calculated from the results of the quantitative fecal fat measurement in conjunction with the dietary fat intake.

CFA will be calculated by using 2 data points:

- Fat consumption in grams as provided by the qualified dietitian at each site.
- Fat excretion in grams/24h as provided by the central laboratory.

CFA will be calculated as follows:

$$\frac{(\text{Grams/24h of fat consumed} - \text{Grams/24h of fat excreted}) \times 100}{\text{Grams/24h of fat consumed}}$$

The primary efficacy endpoint analysis will use the mITT population and be analyzed as randomized. For the analysis of CFA, if a subject switches study treatments (i.e. MS1819 to PERT or PERT to MS1819) during the confinement period, prior to the end of the stool collection, then the CFA value during that confinement period will be excluded from the analysis. The primary method for the analysis of the primary efficacy endpoint will be based on a mixed model. Missing CFA values will not be imputed.

The mixed model will include terms for sequence (MS1819-PERT, PERT-MS1819), random patient nested in sequence, period (1, 2), treatment (MS1819, PERT), and gastric acid suppression use (Y, N). The mixed model will be implemented using SAS® Proc MIXED, as shown in the model code below. The DDFM=KR option denotes the Kenward-Roger method for the denominator degrees of freedom. The variable GASTFL in the code below is the gastric acid suppression use flag (Y, N).

```
PROC MIXED;  
  CLASS SUBJECT SEQUENCE PERIOD TREATMENT GASTFL;  
  MODEL CFA = SEQUENCE TREATMENT PERIOD GASTFL /  
    DDFM=KR;  
  RANDOM SUBJECT(SEQUENCE);  
  LSMEANS TREATMENT / CL DIFF;  
  RUN;
```

The 95% CI of the difference in CFA for MS1819-SD minus CFA for porcine PERT will be used to assess the primary objective. Non-inferiority of MS1819-SD to porcine PERT is achieved if the lower bound of the 95% CI of the difference is greater than -15%,

where 15% is the non-inferiority margin. If non-inferiority is achieved, then superiority will be tested.

The carryover effect will be estimated and tested. If there is a notable carryover, the primary endpoint analysis will be reported for each period separately.

The least squares (LS) means, 95% CIs of the LS means, and the SEs by treatment group will also be presented. In addition, CFA at the end of the first period (Visit 6) and CFA at the end of the second period (Visit 9) will also be summarized by treatment group using descriptive statistics.

Fat consumed (g/24h), fat excreted (g/24h), and CFA (%) will be listed by visit for all subjects in the mITT population.

Details of each supervised confinement, including controlled diet and marker-to-marker stool collection, will be listed for all subjects in the mITT population.

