## 10. STATISTICAL METHODS

### 10.1 General Considerations

**The statistical methods will be further detailed in the Statistical Analysis Plan (SAP).**

Any change to the data analysis methods described in the protocol will require an amendment only if it changes a principal feature of the protocol. Any other change to the data analysis methods described in the protocol, and the description for making the change, will be described in the SAP and in the clinical study report. Additional exploratory analyses of the data will be conducted as deemed appropriate.

Statistical methodology and analyses will be in accordance with the principles outlined by the International Council for Harmonisation (ICH) E9 guidelines.

Tables, listings, and figures will be produced in accordance with the principles outlined by the ICH E3 guidelines.

Summaries will consist of descriptive statistics including the nonmissing counts, mean, standard deviation, median, Interquartiles (IQ), minimum and maximum values for continuous variables, and number and percentage of patients in each defined category for categorical variables.

Statistical tests will be performed at a one-sided 2.5% alpha. However, for the purposes of simplicity and clarity, displays will utilize the equivalent two-sided 5% nominal significance level along with 95% two-sided confidence intervals (CI). The primary goal of the study is to establish the safety of the chosen dose level; with the sample size, it is not anticipated that inferential statistics will achieve significance.

There will be no adjustment for multiplicity arising from secondary efficacy analyses of the primary endpoint and/or secondary endpoint testing. The primary efficacy analysis of the primary endpoint aims to compare the efficacy of MS1819 vs porcine PERT.

As a general rule, missing data will not be replaced.

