2.6 Sample Size Determination

The primary objectives of the trial are to assess the safety of MS1819 and whether the efficacy of MS1819 is noninferior to porcine PERT. The sample size was primarily selected to be sufficient to address the safety objectives of this trial. Given the sample size, efficacy will be assessed with the understanding that adequate power for assessing efficacy would only be achieved for differences that are more favorable than expected.

With regard to safety assessment, at least 30 patients completing both periods are judged enough to adequately assess safety. Any event not occurring in the study would have a 95% CI on the rate extending from 0% to 10%; thus events not occurring may be assumed to be uncommon in the population (<10%).

With regard to efficacy, the primary objective is to show that the efficacy of MS1819, measured on the primary endpoint (ie, the CFA), is noninferior to porcine PERT.

- The noninferiority is chosen equal to 15% and the rationale for this choice is as follows: the difference in mean change from baseline in CFA between the reference and placebo was found to be approximately 32.6% in Trapnell (2011). According to the guidance on Noninferiority Clinical Trials to establish effectiveness (2016), the noninferiority (NI) margin should preserve a specified fraction of the difference between the reference and placebo. A NI margin of 15% preserves 54% of the estimated difference between the reference and placebo.
- In a recent unpublished trial, the standard deviation of the change in CFA was found to be around 16% among patients with a baseline CFA at or above 80%. As some patients enrolled in this trial might have a CFA under porcine PERT lower than 80%, a higher standard deviation of around 20% is expected.
- Because the patients enrolled in the trial are already stabilized on porcine PERT, it is expected that the difference in CFA means between MS1819 and porcine PERT slightly favors PERT, which is expected to be around -8%.

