4.2 Per-Protocol Population

The per-protocol (PP) population is a subset of the mITT population and includes all mITT subjects without major protocol deviations that could impact the efficacy analyses. Subjects who are found to be <80% compliant with MS1819 will be excluded from the PP population. The PP population will be used as supportive to the mITT population.

Prior to database lock, the protocol deviations will be reviewed and the PP Population will be determined. Subjects will be included in the treatment sequence to which they were randomized regardless of the actual treatment sequence received.

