7. MEASUREMENTS OF TREATMENT COMPLIANCE

Treatment compliance will be summarized for MS1819-SD in terms of mg/day using a compliance rate. Given that subjects were to take the dose associated with their pre-study PERT during treatment with PERT, detailed pill information was not collected and thus compliance rate for PERT will not be summarized.

The compliance rate for MS1819-SD will be calculated as:

$$[\text{Actual Dose mg/day} / \text{Expected Dose mg/day}] * 100$$

The actual dose (mg/day) a subject received will be calculated as:

$$[(\text{number pills dispensed} - \text{number of pills returned}) * 140 \text{ mg}] / \text{number of actual study days on MS1819-SD},$$

where the number of actual study days on MS1819-SD is calculated as:

$$((\text{date/time of last MS1819-SD dose} - \text{date/time of first MS1819-SD dose}) / 86400) + 1.$$

The expected dose for MS1819-SD is 2240 mg/day.

Treatment compliance will be summarized by each study period and overall for MS1819-SD using descriptive statistics.

As described in Section 4.2, subjects found to be <80% compliant with MS1819-SD will be excluded from the PP population.

Individual data for study drug (number of pills) dispensed and returned and treatment compliance will be listed for all subjects in the mITT population.

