9.2.1.1 Supportive Analyses of the Primary Efficacy Analysis

A secondary (supportive) analysis to the primary method for the analysis of the primary efficacy measure will be conducted using the per-protocol population, according to randomized treatment group. For this analysis, LS means, 95% CIs of the LS means, SEs of the LS means, LS mean estimate of the treatment difference (MS1819-SD minus porcine PERT), SE of the difference, and 95% CI of the difference will be displayed.

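### No pre-specified analysis tests whether a noninferiority claim on CFA would survive loss of MS1819 values that is related to poor absorption

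*SAP*

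**What the plan says.** SAP 9.1.1 sets the general rule: "Missing data will not be replaced". SAP 9.2.1 repeats it for the primary endpoint, "Missing CFA values will not be imputed", and adds that if a patient changes study treatment in confinement before the stool collection ends, "then the CFA value during that confinement period will be excluded from the analysis". That rule covers switches in either direction.

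The primary analysis is a mixed model in the mITT set, which requires a dose of treatment and at least one complete stool collection (SAP 4.1). Noninferiority is claimed if the lower 95% bound for MS1819 minus PERT is above -15, and superiority is then tested.

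The only supportive analysis of this result (SAP 9.2.1.1) "will be conducted using the per-protocol population, according to randomized treatment group". That population is a subset of mITT, and SAP 4.2 adds: "Subjects who are found to be <80% compliant with MS1819 will be excluded from the PP population". There is no matching rule for PERT, because "detailed pill information was not collected and thus compliance rate for PERT will not be summarized" (SAP 7).

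On the likelihood of a claim, Protocol 10.1 says that "it is not anticipated that inferential statistics will achieve significance", and SAP 2.6 says that "adequate power for assessing efficacy would only be achieved for differences that are more favorable than expected".

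For symptoms, Protocol 10.3 assigns all efficacy endpoints to the ITT set (randomized and dosed), and Protocol 7.3.4 places withdrawn patients who received study product in that analysis. SAP 9.2.2.3 tabulates and lists symptoms in mITT only. SAP 11.1 does not list the change.

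**The concern.** A likelihood-based mixed model without imputation is unbiased if values are lost at random, or if the loss is explained by values that were observed. It is not unbiased if an MS1819 value is missing because that same unobserved value would have been low. The remaining MS1819 values would then look too good, and the difference would move towards noninferiority.

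Such loss is plausible without being stated. The trial is open-label, patients enter stable on PERT, the plan expects MS1819 to be about 8 points worse, and SAP 2.2 notes that malabsorption symptoms can appear within days of a change of enzyme. Other causes are equally open: the plan's 20% dropout is not described as differing by treatment, and a collection can be incomplete because the dye marker passes slowly (Protocol 8.3.3.1).

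At stake is what a reader could conclude from a positive result. The planned outputs would show how many values are missing. No pre-specified analysis would say whether the claim depends on them.

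**Working it through.** **Inputs.** From SAP 2.6: SD of paired differences 20, margin 15, one-sided alpha 0.025, 30 completers, 38 randomized, 20% dropout, expected difference about -8, power computed at -4, PERT-placebo difference 32.6. Assumed: the number, direction and mechanism of losses, and a within-patient correlation of 0.3 or 0.5.

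**1. The plan's own figure.** Standard error 20/√30 = 3.651. At a true -4 the noncentrality is 11/3.651 = 3.01, and the noncentral t with 28 df gives power 82.8%, consistent with the stated figure of around 80%. Also 30/0.8 = 37.5, so 38 randomized. The sample size is not in dispute.

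**2. When a claim arises.** The observed difference must exceed -15 + t(0.975, n-2) × 20/√n.

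- n = 30: -15 + 2.048 × 3.651 = -7.52
- n = 34: -15 + 2.037 × 3.430 = -8.01
- n = 38: -15 + 2.028 × 3.244 = -8.42

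At an observed -8 with 30 completers the bound is -8 - 7.48 = -15.5, so the claim already fails. With 30 completers the chance of a claim is 82.8% at a true -4, 66.3% at -6 and 45.7% at the expected -8.

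**3. False-claim rate at a true -15 (nominal 2.5%).** This is a simulation of 38 patients, 4,000 runs per cell. The REML model has sequence, period, treatment, random patient and an acid-suppression flag (50% assumed), with df = complete pairs minus 2. Four patients are lost on MS1819 and four on PERT. A period-1 dropout loses both values; a period-2 dropout keeps the first.

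| Loss on MS1819 | Rate, corr. 0.3 / 0.5 | Mean estimate |
|---|---|---|
| No loss | 2.9% / 2.5% | not tabulated |
| Random | 2.7% / 2.6% | -15.1 / -15.0 |
| Chance of loss doubles per SD lower MS1819 CFA | 4.2% / 4.6% | -14.0 / -14.0 |
| Chance of loss triples per SD lower | 6.8% / 5.8% | -13.5 / -13.6 |
| Two lowest lost, two random | 6.0% / 6.4% | -13.5 / -13.5 |
| Four lowest lost | 13.0% / 11.2% | -12.2 / -12.4 |

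The Monte Carlo standard error at 12% is √(0.12 × 0.88/4000), about 0.5 point.

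**4. Tipping points.** Let m of 38 patients lack a complete pair. The mean difference in those patients that removes the claim is (38 × threshold - (38 - m) × observed)/m. Example with m = 8, observed -4 and the completers' standard error: (38 × -7.52 + 30 × 4)/8 = -20.7. Each cell below uses, in order, the completers' standard error, the standard error for n = 38, and multiple imputation with Rubin's rules.

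| Observed | 8 lost | 4 lost |
|---|---|---|
| -4 | -20.7; -25.0; -19.3 | -42.1; -46.0; -35.3 |
| -6 | -13.2; -17.5; -12.9 | -25.1; -29.0; -23.0 |
| -7 | -9.5; -13.7; -9.4 | -16.6; -20.5; -15.9 |

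At an observed -4 with four lost, every tipping point lies beyond -32.6, so the claim stands. At -7 with eight lost, a mean of about -9 to -14 in the lost patients removes it.

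**5. Symptoms.** Scores are taken by telephone at Visits 4 and 5 (Protocol 8.2.2). A patient in either sequence who leaves before a complete Visit 6 collection is outside mITT, so those scores reach neither the symptom tables nor the symptom listing. Under Protocol 9.1.1, nonserious worsening of EPI goes on an EPI form and not on the AE form; serious worsening is reported as an SAE.

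**The case against.** The strongest reply is that the point is doubly conditional: noninferiority must be claimed, and MS1819 values must have been lost because they were poor. The trial was sized mainly for safety, and the plan plays down its own inference. This limits the weight of the point. It does not remove it, because the claim rule and the superiority step are still in SAP 9.2.1.

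The false-claim rates are computed at a true -15, not at the expected -8. At a true -8, MS1819 is inside the margin and a claim would not be false. That is correct, and it is why the rates are illustrations and not forecasts.

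A rough tipping point needs only the estimate, its interval and the counts, all of which are planned, and SAP 1 allows additional analyses. This too is correct. What is lacking is a model-based version fixed before the result is known.

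A reader might go further and infer that the plan tilts the trial towards noninferiority. The documents do not support that: no direction of loss is stated, the switch rule is symmetric, and the mixed model keeps patients with one value. Putting the full 20% loss on MS1819 gives rates of 11-30%, and losing the eight worst differences gives about 66%, but nothing in the plan says that loss will fall that way. Nor does the move from ITT to mITT alter the CFA estimate, since a patient with no CFA contributes nothing to it. Losses are not hidden either: counts by visit and treatment, confinement listings and withdrawal reasons are planned (SAP 3, 5.1, 9.2.1).

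**Conclusion.** The gap is real and modest. The primary analysis assumes that losses are ignorable given the observed CFA values, and the per-protocol analysis cannot test this because it restores none of the missing values and may remove further patients on MS1819 compliance alone. If loss is moderately related to low MS1819 CFA, the false-claim rate at a true -15 rises from about 2-3% to 4-7%. It reaches about 11-13% only in the extreme case of losing the four lowest values. These figures rest on the plan's SD, margin and dropout, and on an assumed loss mechanism, split and correlation.

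If noninferiority is not met, nothing changes. If it is met clearly with few losses, the check would clear it. It matters for a claim near the threshold with losses close to the planned 20%. The symptom tables are a separate, smaller point: early leavers' scores are collected and then left out.

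**What to change.** In SAP 9.2.1.1, pre-specify one delta-adjusted (tipping-point) analysis in all randomized and dosed patients, run only if noninferiority is met:

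- Multiply impute missing CFA from the planned model. Lower only the imputed MS1819-period values, in steps from zero until the imputed difference from PERT reaches -32.6.
- Report the shift at which the lower bound crosses -15, as context and not as a second pass/fail rule.
- Show results with and without the switch-excluded values among those imputed.

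Tabulate missing and excluded CFA by treatment, period and recorded reason. Separately, run the malabsorption symptom tables in all dosed patients (the protocol's ITT set), so that Visit 4 and 5 scores of early leavers are kept. Listing the change from ITT to mITT in SAP 11.1 is housekeeping only.

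The cost is SAP wording, one conditional analysis, one count table and a change of population for the symptom tables, all from data already collected. The primary analysis, visits and patient numbers are unchanged. The downside is a little more analysis work, and a positive result may look less secure.

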- Incomplete correction of the lipid malabsorption, which can only be reached by high doses of enteric coated enzyme therapy in approximately 50% of patients with EPI caused by chronic pancreatitis and/or pancreatectomy [Dominguez-Munoz et al, 2006; Safdi et al, 2006]. An internal survey based on all publicly available individual data show that only 25% of patients affected by CF with EPI had fully normalized coefficient of fat absorption (CFA) (ie, CFA higher than 93%) on porcine PERT substitution therapy. The incomplete enzymatic activity of porcine PERTs in the physiochemical environment of the upper digestive tract explains their reduced efficacy. A number of factors are involved, including the gastric acid pH in the range of 1 to 4; the intestinal pH ranging from 4 to 6 (porcine PERTs are active at pH > 6.5 in presence of biliary salts); and the protease content of the upper digestive tract (i.e., gastric pepsin).
- The hazard of zoonotic pathogen transmission to humans remains possible with porcine PERTs because of their animal origins. For example, the porcine parvovirus may be present in these extracts, with (minimal) risk that it can cross species and transmit diseases to humans (Cherney, 2008).

- Most pancreatic enzyme products are unstable. To compensate for enzyme degradation over time, most manufacturers currently include overfill in the finished product. Therefore, their composition is poorly standardized and results in large 'lot-to-lot' variation of efficacy and composition. As product instability requires the product to be stored at cool temperatures, efficacy can decrease once the bottle is open (eg, 6 months for Creon®).
- Some additional concerns identified with porcine PERTs include irritation of oral mucosa if chewed/retained and hyperuricemia because of the presence of purines in porcine pancreatic extracts [Package insert Creon, Pancreaze, Zenpep, Pertzye]. In addition, patients with an allergy to proteins of porcine origin may have severe allergic reactions.
- Because all of the currently marketed PERTs are porcine derived, there is a supply risk (both quality and quantity) that is dependent on the availability of pig herds.

Because of the risks and limitations of porcine PERT, new drugs are demanded by pharmaceutical regulatory agencies and patient associations.

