### **Secondary Analysis:**

The same analysis as described above will be performed in the PP set.

**Subgroup analyses:** Analyses of CFA considering the same approach used for the primary set will be performed in the following subgroups:

- by CFA level while receiving porcine PERT (<80% vs  $\geq 80\%$ ). Of note, it is expected that about 75% of enrolled Patients will have CFAs while receiving porcine PERTs of 80% or greater. An analysis will be done in the subgroup of Patients with CFA below 80% while receiving porcine PERT, as well as in the subgroup of patients with CFA of 80% or greater while receiving porcine PERT.
- By those receiving versus not receiving gastric acid suppression.

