Out of an abundance of caution, the planned sample size is limited to roughly 30 subjects completing. With regard to safety assessment, 30 patients completing both periods are judged enough to adequately assess safety. However, assuming a standard deviation of 20% for the paired differences in CFA measurements within each patient, a noninferiority margin of 15%, a more favorable than expected difference of -4.0% in CFA means between MS1819 vs porcine PERT that favors PERT, a sample size of 30 patients completing both periods will provide a power of around 80% to show noninferiority of MS1819 to porcine PERT at the 0.05 2-sided nominal 0.05 level of significance (that is, a one-sided alpha of 0.025). Accounting for a 20% dropout rate, 38 patients will be sufficient to achieve a power of at least 80%.

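### The primary mixed-model code bounds the patient variance at zero, so the noninferiority interval is too narrow if CFA on MS1819 and on PERT is uncorrelated or negatively correlated within patients

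*SAP*

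**What the plan says.** SAP 9.2.1 analyses CFA in a mixed model with sequence, period, treatment and gastric acid suppression use as fixed terms and patient within sequence as a random term. The printed code has no options on the `PROC MIXED` line, asks for Kenward-Roger degrees of freedom, and specifies the covariance only through the statement that begins "RANDOM SUBJECT(SEQUENCE". There is no `NOBOUND` option and no `REPEATED` statement. Protocol 10.7.1 describes the same random patient term in words. Neither document says what happens if the patient variance is estimated at zero.

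The decision rests on one limit of one interval (SAP 9.2.1): "Non-inferiority of MS1819-SD to porcine PERT is achieved if the lower bound of the 95% CI of the difference is greater than -15"%. Protocol 10.1 fixes the error rate: "Statistical tests will be performed at a one-sided 2.5% alpha".

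The sample size in SAP 2.6 is built on paired differences, "assuming a standard deviation of 20% for the paired differences in CFA measurements within each patient", with "a noninferiority margin of 15"% and "a more favorable than expected difference of -4.0% in CFA means". Neither document gives the SD of CFA on MS1819 or on PERT, or the correlation between the two.

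**The concern.** A random patient intercept whose variance cannot fall below zero can represent only a zero or positive correlation between a patient's two CFA values. When the data show less variation between patient means than within patients, the estimate is set to zero. The model then treats the two values as independent and pools the two sources of variation. The standard error of the treatment difference falls below that of the paired differences, and its degrees of freedom rise.

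With complete pairs this works in one direction only: the bounded standard error can be smaller than the paired one but never larger, so the effect does not average out over trials. Kenward-Roger does not repair it, because at the bound the patient variance has dropped out of the model. At stake is the lower confidence limit that decides noninferiority, and with it the stated one-sided 2.5% error.

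That the procedure bounds variance components at zero by default is a property of the software. The documents show only that nothing in the code overrides it.

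**Working it through.** **Inputs.** SD of paired differences 20, margin 15, planning difference -4, expected difference -8, 30 completers, 20% dropout (SAP 2.6); 1:1 allocation (SAP 2.5), taken as 15 completers per sequence; one-sided error 2.5% (Protocol 10.1); model terms (SAP 9.2.1). The correlation rho between CFA on the two treatments is not given, so it is varied. Equal variances and normal errors are assumed.

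**The plan's own figure.** The SE of the mean paired difference is 20/√30 = 3.651. The noncentrality at -4 is (15 - 4)/3.651 = 3.01, and a t test on 28 df has power 82.8%. Allowing for dropout, 30/0.8 = 37.5, rounded up to 38. Both agree with SAP 2.6. This calculation uses the paired standard error, which the bounded fit does not always use.

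**Mean squares, 30 complete pairs.** Let s² be the variance of one CFA value, so that 400 = 2s²(1 - rho).
- Within patients: expected mean square s²(1 - rho), on 30 - 2 = 28 df.
- Between patients: expected mean square s²(1 + rho), on 30 - 2 - 1 = 27 df (sequence and gastric acid suppression removed).
- Unbounded fit: SE² = 2 × (within mean square)/30, on 28 df, always.
- Bounded fit: the same, unless the between mean square is below the within mean square. Then the two are pooled on 28 + 27 = 55 df.
- Probability that the bound is active: P(F on 27 and 28 df < (1 - rho)/(1 + rho)). At rho = -0.2 this is P(F < 1.5) = 85%.

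**Hand check at rho = -0.2.** s² = 400/2.4 = 166.7. The expected within mean square is 166.7 × 1.2 = 200 and the between one is 166.7 × 0.8 = 133.3. Pooled: (28 × 200 + 27 × 133.3)/55 = 167.3. The SE falls from √(2 × 200/30) = 3.65 to √(2 × 167.3/30) = 3.34, and the t quantile from 2.048 to 2.004. The half-width goes from 7.48 to 6.69, about 11% narrower.

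**Simulation at the margin** (true difference -15, at least 2,000,000 draws per setting):

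| rho | Bound active | Mean CI width, printed code | One-sided error, printed code |
|---|---|---|---|
| -0.4 | 99% | 12.3 | 4.8% |
| -0.3 | 94% to 95% | 12.8 | 4.2% to 4.3% |
| -0.2 | 85% | 13.3 | 3.7% |
| -0.1 | 70% | 13.7 | 3.3% |
| 0 | 50% | 14.1 | 2.9% |
| +0.1 | 30% | 14.5 | 2.7% |
| +0.2 | 15% | 14.7 | 2.6% |
| +0.3 | 6% | 14.8 | 2.5% |

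The unbounded fit has a mean width of 14.8 and an error of 2.5% in every row. Where two values are shown, separate runs differed by rounding or simulation error.

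**Sensitivity.**
- Keeping 28 df at the bound: 2.8% at rho 0 and 3.5% at -0.2.
- 38 completers: 2.9% and 3.7%.
- 30 completers plus 8 patients with period 1 only, full REML fit: 2.9% and 3.7% with equal SDs; 2.8% and 3.1% when one treatment's SD is twice the other's.

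**The case against.** The strongest reply is that nothing in the documents shows the triggering condition. Both CFA values come from the same patient, on the same controlled diet and collection procedure, about three weeks apart, and a positive correlation would be a natural expectation. At +0.2 or more the excess is at most about 0.1 percentage point. This stands.

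A reader might infer a correlation near or below zero from the plan's own figures. Protocol 5.3 reports that "only 25% of patients affected by CF with EPI had fully normalized coefficient of fat absorption" (above 93%), and Protocol 10.7.1 says "it is expected that about 75% of enrolled Patients will have CFAs while receiving porcine PERTs of 80% or greater". Read as the quartiles of one normal distribution, these give a PERT SD of (93 - 80)/1.349 = 9.6. The implied correlation is then (sM² + 9.6² - 20²)/(2 × sM × 9.6), where sM is the MS1819 SD: -0.29, about 0 and +0.24 for sM of 15, 17.5 and 20. The documents do not support this as an estimate:
- The first figure is an internal survey of public data. The second is an expectation for patients enrolled here. Neither document joins them or states a normal shape.
- CFA cannot exceed 100%, yet that normal curve puts about 8% of patients above it. A lognormal shape for fat excretion with the same quartiles gives a PERT SD of about 14.6, and correlations of +0.09, +0.23 and +0.37.
- The MS1819 SDs appear nowhere in the documents.
- The paired SD of 20 is a planning value set above an observed 16. With 16 and a PERT SD of 9.6, the correlation is +0.21 at sM 15 and +0.42 at 17.5. The 16 comes from patients with baseline CFA of 80% or more, so this shows sensitivity only.

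The consequence is also limited. SAP 2.6 says the sample size was chosen mainly for safety, Protocol 10.1 does not expect inferential statistics to reach significance, and power at the expected -8 is about 46% with the unbounded fit. That lowers the priority, but the SAP still tests noninferiority at a stated error rate.

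**Conclusion.** The weakness is real but conditional. As printed, the code holds one-sided 2.5% only if the within-patient correlation of CFA is clearly positive. The excess is about 0.4 percentage points at correlation 0 and 1.2 at -0.2, and negligible from +0.2 upwards. These sizes rest on 30 complete pairs, normal errors and equal variances; with unequal variances and single-period patients the excess at -0.2 was smaller (3.1%). The sign of the correlation cannot be settled from the documents, so inflation in this trial is not shown. Because the remedy costs almost nothing and makes the error rate independent of the unknown correlation, it is worth making as a cheap improvement before any analysis. Choosing afterwards could change the noninferiority result.

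**What to change.** In SAP 9.2.1 write `PROC MIXED NOBOUND;`. Use the same statement for CNA, whose analysis SAP 9.2.2.1 models on the primary one. State that a negative patient variance estimate will be kept and reported. Keep all mITT patients in the model, including those with one usable period.

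Do not replace the primary model with an analysis of within-patient differences. It gives the same interval for complete pairs, but it drops single-period patients, whom SAP 4.1 includes. With the planned dropout that could be up to 38 - 30 = 8 patients.

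Cost: one word of code and one sentence of text. The CI is somewhat wider when the bound would have been active (mean width over all trials 14.8 instead of 14.1 points at correlation 0, and instead of 13.3 at -0.2). With complete pairs it is otherwise unchanged. Power at -4 with 30 completers is 82.8%, still consistent with the planned figure of around 80%.
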